2.6.2.5 Control of Familywise type I error rate

1-sided p-values and alpha level of 0.025 are considered for the testing procedure.

[figure not shown]
Hypotheses are grouped into three families. The first family contains the primary hypothesis H_{01} . The second family contains two secondary hypotheses H_{02} and H_{03} . The third family contains the remaining secondary hypotheses H_{04} , H_{05} and H_{06} . A hierarchical testing strategy is applied to these three families to control the familywise type I error rate in the strong sense. First H_{01} is tested at level α . If it is rejected, we test the second family using a closed test at level α . If both hypotheses are rejected, we test the third family using the Hommel procedure at level α . When not all hypotheses in a family can be rejected, testing stops at the corresponding family and does not proceed to test the next family.

Within the second family, a closed test procedure based on weighted Simes tests is applied with 80% weight for H_{02} and 20% weight for H_{03} . First the two nominal p-values for the two hypotheses are simultaneously compared to α . If both nominal p-values are less or equal α , the two null hypotheses are rejected. Otherwise the individual nominal p-values will be compared to the pre-specified weighted alpha. If the p-value for H_{02} is less or equal 0.8α , H_{02} is rejected; if the p-value for H_{03} is less or equal 0.2α , H_{03} is rejected.

Within the third family, the Hommel procedure is applied. Let the ordered p-values for H_{04} , H_{05} and H_{06} be $p(1) \leq p(2) \leq p(3)$ and the corresponding hypotheses $H(1)$, $H(2)$ and $H(3)$. First if $p(3)$ is less or equal α , we can reject all three hypotheses. Otherwise, if $p(2)$ is less or equal $\alpha/2$, we can reject $H(2)$ and $H(1)$. Otherwise, if $p(1) \leq \alpha/3$ or ($p(1) \leq \alpha/2$ and $p(2) \leq 2\alpha/3$), $H(1)$ is rejected.

For more details see also [Figure 2-2](#).

Figure 2-2 Applied testing procedure

2.6.3 Handling of intercurrent events

For the secondary estimand we consider the same intercurrent events as for the primary estimand (see [Section 2.5.3](#)). Except one specific exception described below, the proposed approach for all secondary endpoints for the intercurrent events of discontinuation of investigational treatment, the use of PCSK9 targeting non-study medication or lipid apheresis or the impact of the COVID-19 pandemic is the treatment policy strategy. For the intercurrent event of death a while alive strategy will be applied.

The first secondary endpoint of relative change (percentage change) from baseline to mean LDL-C level over the double-blind study period (averaged over all post baseline visits) will be handled differently for the use of PCSK9 targeting non-study medication or lipid apheresis. For this specific intercurrent event for this endpoint a hypothetical strategy will be applied.

If an assessment at a visit is affected by multiple intercurrent events, strategy for the intercurrent events occurring will be applied considering the following order of decreasing importance: first hypothetical, followed by while alive and treatment policy. For treatment policy, for the remaining missings PCSK-9 (MAR imputation) is considered over second treatment discontinuation (J2R imputation).

2.6.4 Handling of missing values not related to intercurrent event

Missing values will be under a missing at random (MAR) assumption for every secondary endpoint. For the relative change from baseline to the mean LDL-C level over the double-blind study period (first secondary endpoint), the change from baseline in SF-BPI pain severity score at Day 360 (fourth secondary endpoint) and the change from baseline in SF-BPI pain interference

score at Day 360 (fifth secondary endpoint) a multiple imputation approach will be applied as described in [Section 5.5.3](#). The annualized number of days participants experiencing self-reported pain from Day 1 to Day 360 (third secondary endpoint) will be handled by normalizing the observation time via the offset function. In case of missing values muscle-related AE / SMQ rhabdomyolysis / myopathy will not be imputed but analyzed according to last known status of the occurrence of an event.

2.6.5 Sensitivity analyses

To investigate the sensitivity to missing values or potentially different observation times in the two study arms, a time to the first experience of at least one muscle-related AE as defined in the SMQ rhabdomyolysis / myopathy will be conducted via a Cox proportional hazards model (see [Section 5.5.2.5](#)).

The event-free observation time per participant will be censored at the earlier date out of death date, last contact date and date of visit Day 360. This covers intercurrent event strategies: for participants with an intercurrent event following the while alive strategy (time of censoring will be set to the time of the intercurrent event (i.e. date of death)) and for intercurrent events following the treatment policy strategy no censoring will be assumed for the intercurrent event itself is applied.

2.6.6 Supplementary analyses

2.6.6.1 Descriptive statistics

Descriptive summaries will be provided for the secondary endpoints.

2.6.6.2 CCI

CCI

2.6.6.3 CCI

CCI

2.6.6.4 CCI

2.6.6.5 Subgroup analysis

Regarding subgroup analysis for secondary endpoints see [Section 2.6.1](#).

2.7 Safety analyses

All safety parameters will be analyzed based on the SAF, including the secondary safety endpoint.

All listings and tables will be presented by treatment group. Safety summaries (tables, figures) include all data from the double-blind treatment period (i.e. post-baseline assessments) and baseline data.

2.7.1 Adverse events (AEs)

A treatment-emergent adverse event (TEAE) is defined as any adverse event (AE) that started after the start of blinded investigational treatment injection or was present prior to start of double-blind treatment but increased in severity after the start of blinded investigational treatment injection. If the AE start date is the same as date of injection but time is not available for comparison, the AE will be considered to be treatment emergent.

All information obtained on AEs will be displayed by treatment group and participant.

The number (and percentage) of participants with TEAEs will be summarized in the following ways:

- by treatment, primary system organ class and preferred term.
- by treatment, primary SOC, PT and severity.
- by treatment, Standardized MedDRA Query (SMQ) and PT. SMQ lowest hierarchy level broad search will be presented.

Unless otherwise stated, SOC's will be sorted alphabetically and, within each SOC, the PTs will be sorted in descending order of frequency in the inclisiran column.

Separate summaries will be provided for study medication related AEs, SAEs, , AEs leading to discontinuation of study treatment, and AEs leading to discontinuation of study.

A participant with multiple AEs within a primary system organ class or preferred term is only counted once towards the total of the primary system organ class or preferred term, respectively.

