10.1 Definition of adverse events and reporting requirements

10.1.1 Adverse events

An AE is any untoward medical occurrence (e.g. any unfavorable and unintended sign [including abnormal laboratory findings], symptom or disease) in a clinical investigation participant after providing written informed consent for participation in the study. Therefore, an AE may or may not be temporally or causally associated with the use of a medicinal (investigational) product.

The investigator has the responsibility for managing the safety of individual participants and identifying AEs.

Novartis qualified medical personnel will be readily available to advise on trial related medical questions or problems.

The occurrence of AEs must be sought by non-directive questioning of the participant at each visit during the study. Adverse events also may be detected when they are volunteered by the participant during or between visits or through physical examination findings, laboratory test findings, or other assessments including PROs and diary (refer to [Section 8.5.1](#)).

AEs must be recorded under the signs, symptoms, or diagnosis associated with them, accompanied by the following information (as far as possible) (if the event is serious refer to [Section 10.1.2](#)):

1. The severity grade:
 - mild: usually transient in nature and generally not interfering with normal activities
 - moderate: sufficiently discomforting to interfere with normal activities
 - severe: prevents normal activities

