12.5.3.1 Adverse events

All information obtained on AEs will be displayed by treatment group and participant.

The number (and percentage) of participants with TEAEs (events started after the first dose of study medication or events present prior to start of double-blind treatment but increased in severity based on preferred term) will be summarized in the following ways:

- by treatment, primary system organ class and preferred term.
- by treatment, primary system organ class, preferred term and maximum severity.
- by treatment, Standardized MedDRA Query (SMQ) and preferred term.

Separate summaries will be provided for study medication related AEs, death, SAEs, other significant AEs leading to discontinuation

A participant with multiple AEs within a primary system organ class is only counted once towards the total of the primary system organ class.

AEs which will be counted for a specific treatment period are those which are treatment-emergent. These events are those with an onset after the start of the treatment period, or which were present prior to the start of the treatment period but increased in severity, changed from being not suspected to being suspected of study drug relationship, or developed into SAEs after the start of the treatment period.

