Analysis of adverse events will be done for TEAEs. Protocol section 12.5.3 describes that additionally, all summary tables for AEs will be repeated for on-treatment AEs only (TEAEs). This repetition will not be done.

First dose of double-blind treatment (Day 1) will be considered for the analyses, even if protocol mentions time of randomization. Day 1 and randomization date of some participants may not be the same, therefore Day 1 is considered for consistency of the analyses.

There will not be a separate table for exclusions from the analyses set, as there are no PDs defined excluding participants from an analysis set and exclusions are covered by the definition of the analyses set. Therefore, analysis would be redundant with other tables.

Region and country will not be summarized for the randomized set, countries are summarized on the FAS.

Supplementary analyses presenting relative risk and risk difference will be presented using CMH with Mantel-Haenszel estimators for both measures and will not be based on score statistics.

Descriptive summary of all vital signs data will not be provided, number and percentages of participants with notable abnormal vital signs will be provided instead. Listing of vital signs will be limited to the notable abnormal vital signs.

5 Appendix

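### SAP 2.7.1 adopts the narrower of two conflicting treatment-emergent definitions in Protocol 12.5.3.1 without saying so, so some events that turn serious or drug-suspected after dosing go uncounted by arm

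*SAP*

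**What the plan says.** Protocol 12.5.3.1 contains two rules. The sentence introducing the treatment-emergent tables has a parenthesis that covers events starting after the first dose and "events present prior to start of double-blind treatment but increased in severity based on preferred term". The closing paragraph of the same section states which events count for a treatment period. It covers new onset and increased severity, and adds earlier events that "changed from being not suspected to being suspected of study drug relationship, or developed into SAEs after the start of the treatment period".

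SAP 2.7.1 covers onset after the first injection, and an event that "was present prior to start of double-blind treatment but increased in severity after the start of blinded investigational treatment injection". It has no causality or seriousness route. It then announces the further tables: "Separate summaries will be provided for study medication related AEs, SAEs, , AEs leading to discontinuation of study treatment", together with events leading to study discontinuation. None of these has a counting rule of its own.

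SAP section 4 states "Analysis of adverse events will be done for TEAEs". It cites the protocol's plan to repeat the tables for on-treatment events and adds "This repetition will not be done". The choice between the two protocol definitions is not listed there.

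**The concern.** Severity, seriousness and causality are three separate assessments in Protocol 10.1.1 and 10.1.2. A rule that uses severity alone cannot detect a change in either of the other two. The data to detect such changes should largely exist. Adverse events are recorded "in a clinical investigation participant after providing written informed consent for participation in the study", and Protocol 10.1.1 requires changes in severity and in suspected relationship to be assessed at each visit.

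At stake is whether the by-arm serious and drug-related counts include every event that the protocol's wider rule would count. Safety and tolerability are part of the trial's stated purpose. A reader of the study report who knows only the closing rule of Protocol 12.5.3.1 would assume that rule had been applied.

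**Working it through.** The plan states no figure on this point, so the check compares the rules.

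**Step 1. Routes by which a pre-existing event becomes treatment-emergent.**

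| Route after treatment starts | Protocol 12.5.3.1, parenthesis | Protocol 12.5.3.1, closing rule | SAP 2.7.1 |
|---|---|---|---|
| Severity increases | yes | yes | yes |
| Not suspected becomes suspected | no | yes | no |
| Becomes serious | no | yes | no |

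Against the closing rule, the SAP keeps 1 of 3 routes and loses 3 − 1 = 2. Against the parenthesis it loses none.

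**Step 2. Test cases.** Each event starts in screening or run-in, non-serious and not suspected, and is kept as one record with its original start date.

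| Grade before first injection | Change after first injection | Closing rule | SAP 2.7.1 |
|---|---|---|---|
| Mild | becomes moderate | counted | counted |
| Mild | still mild, becomes suspected | counted | not counted |
| Moderate | still moderate, hospitalized | counted | not counted |
| Severe | still severe, hospitalized or suspected | counted | not counted |

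**Step 3. Ceiling of the scale.** Protocol 10.1.1 has three grades, of which the top is "severe: prevents normal activities". The number of higher grades available is 2 from mild, 1 from moderate and 0 from severe. An event graded severe at first dose therefore cannot meet the SAP's severity route, whatever happens to it later.

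**Step 4. Which tables are affected.** The treatment-emergent tables follow directly from SAP 2.7.1. For the serious and drug-related summaries the limit comes from section 4, because SAP 2.7.1 does not itself restrict them. The protocol's other set of tables would not have caught these events either: Protocol 12.5.3 limits it to events with a start date in the double-blind period. The treatment-emergent definition is thus their only way into a by-arm count.

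**Step 5. What stays visible.** SAP 2.7.1 keeps a display of all adverse event information by treatment group and participant. SAP 2.7.2 keeps a separate summary and listing of deaths.

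**Step 6. Exposure to the gap.** The event must begin between consent and first injection. That interval is at most about 14 days of screening + 120 of run-in + 10 of baseline = 144 days. Participants already at their maximum tolerated statin dose skip the run-in. The documents give no rate of pre-dose events and no rate of later change in seriousness or causality, so the count cannot be calculated.

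**The case against.** The strongest reply is that the SAP departs from nothing. Protocol 12.5.3.1 has a severity-only definition, placed in the sentence about these very tables, and the SAP carries it over almost unchanged. This stands in part. The protocol conflicts with itself, and the SAP chose one side. What remains is that the choice is not declared and goes against the paragraph that states expressly which events are counted.

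Second, the treatment-emergent limit on the serious and drug-related summaries is an inference. SAP 2.7 says that safety summaries include all double-blind-period and baseline data. That also stands. The section 4 sentence is the more specific of the two, but the SAP should not leave this to interpretation.

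Third, the gap may be small. A mild or moderate event that leads to hospitalization would often be regraded upward and so be counted. Myopathy and marked creatine kinase elevation are exclusions at baseline, and a maximum tolerated statin dose must have been held for at least 30 days before randomization. These points bear on frequency, and none of them closes the gap.

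A reader might go further and infer three things that the documents do not support:

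- That the muscle-related endpoint is undercounted. SAP 2.6.2.2 gives it its own window, from first dose to the earlier of last contact and the Day 360 visit, without using the treatment-emergent definition.
- That muscle complaints present at entry fall into the gap. Protocol 10.1.1 sends conditions present at consent to medical history, so only events arising after consent are concerned.
- That pre-dose events are common here because of statin titration. The run-in is optional and no rate is given.

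**Conclusion.** The point holds as an unresolved conflict within Protocol 12.5.3.1, settled in the SAP without a declaration and in the direction that counts fewer safety events. Followed as written, the SAP omits from the by-arm treatment-emergent tables any event that began between consent and first injection and became serious or suspected afterwards at the same grade. Events already graded severe are omitted by construction. Omission from the serious and drug-related summaries rests on reading SAP section 4 as governing them.

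The conclusion assumes that an event turning serious stays on its original record rather than being entered again with a new start date; the documents do not settle this. The number of events is unknown and may be small. No effect on the primary or confirmatory analyses is shown, and no imbalance between arms. The change is still worth making, because it is cheap and prevents undercounting in the main safety tables.

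**What to change.** In SAP 2.7.1, define a treatment-emergent event as one that starts after the first injection, or one present earlier that afterwards increases in severity, changes from not suspected to suspected, or becomes serious. State that this single definition governs the treatment-emergent, serious and study-medication-related tables. In SAP section 4, record that Protocol 12.5.3.1 contains two definitions and that the wider one is used.

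No protocol amendment is needed. Deleting the shorter protocol definition would require one under Protocol 14.1 and is unnecessary once the SAP declares which rule applies.

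The cost is a short SAP edit, one derivation in the adverse event dataset, and slightly higher event counts. The derivation needs the dates on which seriousness and causality changed, and the documents do not show that these dates are held. Where a date is missing, count the event as treatment-emergent. This matches the SAP's existing convention for an event that starts on the injection date with no time recorded.

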2.7.2 Deaths

A separate summary by SOC and PT of death cause by treatment will be provided. Listing of all deaths will be provided.

2.7.3 Laboratory data

Laboratory data consist of hematology, clinical/limited chemistry, lipid panel and urinalysis measurements.

Notable abnormal laboratory data will be listed by treatment group, participant, and visit/time and if ranges are available, abnormalities will be flagged. Shift tables based on the standard ranges for each laboratory parameter will be provided by treatment group at each visit to present incidence of transitions from a baseline high, normal or low laboratory value to a post-baseline high, normal or low value. Glucose should be measured fasting, non-fasting glucose values will be excluded from the analyses.

Number and percentages of participants with newly occurring or worsening notable liver-function, renal function and skeletal muscle laboratory values as defined in [Section 5.4](#) will be tabulated.

2.7.4 Other safety data

2.7.4.1 Vital signs

Notable abnormal vital signs data will be listed by treatment group, participant, and visit/time and if ranges are available, abnormalities will be flagged.

Number and percentages of participants notable vital sign values at screening and newly occurring or worsening notable values any time post-baseline as defined in [Section 5.4](#) will be tabulated.

2.8 Additional analyses to assess the impact of COVID-19 pandemic

Number and percentage of participants with COVID-19 related protocol deviations will be summarized by deviation term and relationship to the COVID-19 pandemic..

To assess the impact of COVID-19 on safety, and to assess possible regional differences in reporting of AEs, the most frequent AEs will be summarized by preferred term and country.

2.9 Patient-reported outcomes

Analyses of the electronic diary and the SF-BPI are described in [Section 2.6.2.3](#) and [Section 2.6.2.4](#), respectively. The following questionnaires are exploratory objectives for the study:

- Short-Form health survey,
- Gastrointestinal Symptom Rating Scale,
- Treatment Satisfaction Questionnaire for Medication,
- Walking Impairment Questionnaire,
- MacNew Heart Disease Quality of Life Questionnaire.

The pre-processing of the patient-reported outcomes will be described in the following sections for each of the questionnaires.

Compliance to questionnaire completion will be summarized descriptively for each questionnaire.

2.9.1 Short-Form Health Survey

The Short-Form Health Survey (SF-36) is a generic health-related quality of life instrument which comprises of 36 questions across 8 domains (see also Section 8.5.1.3 in Protocol).

The questionnaires will be preprocessed in-house by the sponsor (Novartis). Physical component summary (PCS) and Mental component summary (MCS) will be provided for further analysis for screening, baseline, Day 90, Day 210 and EOT/EOS (Day 360). All analyses will be performed by domain.

The higher the scores, the higher is the quality of life for the participant.

CCI

2.9.2 Gastrointestinal Symptom Rating Scale

The self-administered Gastrointestinal Symptom Rating Scale (GSRS) questionnaire contains 15 items for gastrointestinal syndromes, which are composed of 5 dimensions (abdominal pain, reflux syndrome, indigestion, diarrhea and constipation) and uses a Likert scale with 7 units from 1 to 7 (no discomfort to very severe discomfort, see also Section 8.5.1.4 in Protocol)

The subscores of individual domains are calculated by averaging the scores of the associated items. The average of all subscores gives the total score, which ranges between 1 and 7. The score will be derived for each visit between baseline and EOT/EOS (Day 360).

If there is missing data for a participant and the available data is more than 50% for the corresponding dimension, the missing items will be imputed using the mean score of the non-missing item scores. Else no imputation will be done and the dimension score will be excluded from the analysis (see corresponding Manual).

The lower the value, the better the gastrointestinal condition.

CCI

